Rationale: Initial clinical studies have shown that Dorsal Root Ganglion (DRG) can significantly reduce chronic intractable pain in a variety of chronic pain conditions including Chronic Low Back Pain (CLBP). CLBP as a diagnosis represents a heterogeneous patient population, for which there are few treatments with proven long-term efficacy other than lumbar spinal surgery. This study sets out to evaluate the effectiveness of DRG stimulation in a homogenous sub population of CLBP, that being Discogenic Low Back Pain or Discogenic Pain which is chiefly driven by disruption or deterioration of the lower lumbar intervertebral discs and is believed to represent around 40% of CLBP generally.

Objective: The purpose of this prospective post market observational pilot study is to evaluate the effect of DRG stimulation in the management of chronic discogenic pain in subjects who are refractory to other available treatments. Selected subjects will not be suitable candidates for lumbar spinal surgery and will meet the standard selection process for DRG stimulation as routinely utilised in the study centres. Results from this pilot study will inform current clinical practice and future comparative studies in this specific population.

Study design: This is a prospective, single-arm, multi-centre, post market, observational pilot study to collect data on pain relief, subject satisfaction, quality of life, physical functioning and safety.

Device: Commercially available Spinal Modulation Neurostimulator System for the management of chronic intractable pain (CE 567069). The device will be used within its CE mark indication (intractable chronic pain). However, for this pilot study all devices and associated implantable equipment will be provided at no cost to the study centres as it is not reimbursed yet for this specific sub population of CLBP.

Study population: A maximum of 20 subjects will be enrolled into the pilot study but we will cease enrolment once 15 subjects have had a successful trial and proceeded to full implant. Any patient enrolled at that time will continue through the protocol. The subjects will be of either gender, between 18 and 65 years of age and suffering from confirmed discogenic Low Back Pain (LBP) (minimum duration of 6 months) and are not suitable candidates for lumbar spinal surgery.

Data Collection: Potential subjects will be enrolled after they have read and signed a Patient Informed Consent (PIC) form. Subjects enrolled will be asked to complete several questionnaires prior to their procedure and at routine follow up visits for 12 months.

Follow-up visits: Subjects will visit the hospital for the following visits: Baseline, Trial Neurostimulation (TNS) procedure, End of Trial, Implantable Neurostimulator (INS) implant, 2 week follow-up (FU), 3 month FU, 6 month FU and 12 month FU.

Risks: The implantation of the system is a standard procedure in the participating hospitals and regular follow up visits for the first year after this procedure are also standard practice. While this procedure is not routinely offered to patients with Discogenic Low Back pain due to reimbursement restrictions, the use of the therapy in this patient group falls within the CE

mark indication for the treatment. As participants in this research would not be offered this therapy if they would not be enrolled in this study, a clinical trial insurance is in place to reassure coverage in case of any complications.

Subject who decided not to participate in this study will not receive a neurostimulator and will be monitored by their physician as needed in accordance with standard medical procedures.

1 INTRODUCTION AND RATIONALE

1.1 History of Therapy

Neuromodulation for the treatment of chronic pain has been used for over a century¹. The first use of electricity in the spine for neuromodulation of pain was conducted by Norm Shealy in 1967². The development of spinal cord stimulation (SCS) technology has grown rapidly in the past 40 years and is now used in over 40,000 new patients each year.

1.2 Spinal Cord Stimulation

Several recent systematic reviews have provided evidence that this stimulation technology is a safe and effective treatment option for patients suffering from chronic, intractable pain³⁻⁵. The effective rate of serious complications is quite low³⁻⁵. The treatment has been found to be successful in approximately 50% of patients that have a successful temporary stimulation trial period^{6,7}. In the largest prospective trial published to date, Kumar and colleagues found a significant reduction in leg pain when compared to a conventional medical management control group in the Failed Back Surgery Syndrome (FBSS) population^{6,8}. In a similar manner, Kemler and colleagues found that SCS can be effective in the treatment of complex regional pain syndrome (CRPS)⁹⁻¹¹. Despite varying levels of success in the literature, approximately 50% of patients will not receive adequate pain relief from traditional spinal cord stimulation. The Spinal Modulation Neurostimulation System allows a novel method of Spinal Cord Stimulation by specifically stimulating the Dorsal Root Ganglion (DRG). There are, to date, five published clinical studies on the use of the Spinal Modulation Neuromodulation System that demonstrate that DRG stimulation is a safe and effective treatment for a variety of chronic pain conditions including FBSS and Low Back Pain (LBP) generally¹²⁻¹⁶.

1.3 Therapy Description

DRG stimulation with the Spinal Modulation Neurostimulation System consists of a two-phase treatment process: 1) a trial phase and 2) a permanent implant phase. The first phase involves implanting stimulation electrodes (or “leads”) into the epidural space, which are connected to an external Trial NeuroStimulator (TNS) to electrically stimulate the Dorsal Root Ganglion (DRG). If the subject experiences sufficient pain relief, defined as a reduction in pain intensity of $\geq 50\%$, during this trial stimulation phase they will progress to receive a fully Implantable NeuroStimulator (INS) system (phase 2).

1.4 Rationale

Low Back Pain (LBP) generally and Chronic Low Back Pain (CLBP) particularly, represents a significant clinical challenge with a one year incidence rate of 10-15% and a point prevalence of 15-30% of the US population¹⁷. Incremental healthcare costs attributable to LBP were estimated at \$US 26.3 billion in 1998¹⁸. Furthermore, 75% of costs associated with LBP are accumulated by just 5% of the LBP population further highlighting the need for effective treatment options for CLBP sufferers¹⁹.

Discogenic LBP describes LBP originating from one or more intervertebral discs as depicted below in Figure 1.

[figure not shown]

Figure 1.

The Intervertebral Disc with Innervation.

Image taken from Chapter 15: Discogenic Low Back Pain ([name] et al) in Evidence Based Interventional Pain Medicine – According to Clinical Diagnosis Wiley Blackwell 2012. J. Van Zundert et al

Intervertebral discs can become painful when nociceptive afferent (pain sensing) fibres present in the outer layer of the annulus fibrosus are activated due to disruption of the disc, usually caused by injury or degeneration. Figure 2 shows different degrees of disc disruption as seen during discography (intra-disc injection of dye under fluoroscopy or computerised tomography (CT)).

Discogenic low back pain is believed to account for 26-42% of CLBP²⁰. Currently, aside from spinal surgery, there are few effective treatments for this common, debilitating condition, which justifies the need for further research into potential therapy options²⁰.

[figure not shown]

Figure 2. The Dallas Discogram Scale to Classify Grades of Disc Disruption.

Image taken from Chapter 15: Discogenic Low Back Pain ([name] et al) in Evidence Based Interventional Pain Medicine – According to Clinical Diagnosis Wiley Blackwell 2012. J. Van Zundert et al

Early clinical results on the use of DRG stimulation in LBP are encouraging and in line with other neuromodulation therapies¹²⁻¹⁴. However, the results for SCS in this diverse patient population are generally mixed^{3, 6-8}. We wish to study the effectiveness of DRG stimulation in this homogenous sub-population of CLBP in whom the pathophysiology of chronic pain has been properly elucidated. The neuroanatomical mapping of nociceptive afferent neurons from the lower lumbar (L4/5 and L5/S1) Intervertebral discs through the sympathetic trunk and L2/L1 DRG(s) suggests that these levels may be a good target for interventional therapies²¹. Indeed anecdotal observations from the previously treated populations suggest that this may hold true and as such the L2 and or L1 DRG(s) will be targeted with treatment to assess this.

In 2007 a consensus article was published on the clinical relevance of changes in pain intensity as measured by commonly utilised research instruments such as a visual analogue scale (VAS) and a numerical pain rating scale (NPRS) in chronic pain²². While standard practice is to judge the success of a neurostimulation trial procedure as a reduction in pain intensity of $\geq 50\%$ the mentioned consensus article denotes that a reduction in pain intensity of $\geq 30\%$ or 2 points on a VAS/NPRS is clinically relevant²¹. As such the treatment in this observational post market study will follow standard practice and only subjects who experience $\geq 50\%$ pain relief during the temporary trial procedure will go on to receive the implantable stimulator but we will judge the long term effectiveness of the therapy against the $\geq 30\%$ or 2 point reduction as recommended.

© 2013 Pearson Education, Inc. All Rights Reserved. May not be copied, scanned, or duplicated, in whole or in part. Due to electronic rights, some third party content may be suppressed from the eBook and/or eChapter(s). Editorial review has determined that any suppressed content does not materially affect the overall learning experience. Pearson Education, Inc. reserves the right to remove additional content at any time if subsequent rights restrictions require it.

1 2 3 4 5 6 7 8 9 10 11 12 13 14 15 16 17 18 19 20 21 22 23 24 25 26 27 28 29 30 31 32 33 34 35 36 37 38 39 40 41 42 43 44 45 46 47 48 49 50 51 52 53 54 55 56 57 58 59 60 61 62 63 64 65 66 67 68 69 70 71 72 73 74 75 76 77 78 79 80 81 82 83 84 85 86 87 88 89 90 91 92 93 94 95 96 97 98 99 100

3. STUDY DESIGN

This is a prospective, observational, multi centre, single arm pilot study designed to assess the effectiveness of DRG stimulation using the Axium® SCS system for the treatment of discogenic LBP over a 12 month follow up period.

Eligible subjects for DRG stimulation will be asked to participate in this study. If they decide to participate, they will be treated with the Axium® SCS system and prospectively followed for 12 months following implantation. If they decide not to participate, they will not receive the Axium® SCS system and will be monitored by their physician as needed in accordance with standard medical procedures.

In line with standard practice the system will be implanted in two stages. The first stage is the Trial NeuroStimulation (TNS) phase during which epidural leads are implanted at the L2 and/or L1 level (to treat the back pain) and L3 and/or L4 to treat any leg pain and temporarily tunnelled to an external trial stimulation device. Subjects will then utilise the temporary system for period of time in line with usual practice (typically 5-10 days). If, at the end of this TNS phase, the subject has experienced a reduction of $\geq 50\%$ in their LBP they will proceed to the second treatment stage when the Implantable NeuroStimulator (INS) will be implanted and connected to existing epidural leads. Following INS insertion subjects will be followed prospectively for 12 months as shown in Figure 3 below

[figure not shown]

Figure 3: Study Flowchart; Questionnaires administered at the Follow Up (FU) visits in blue and the final 12 month visit

4 STUDY POPULATION

4.1 Population

A maximum of 20 subjects will be enrolled but we will cease enrolment once 15 subjects have had a successful trial and proceeded to full implant. Any patient enrolled at that time will continue through the protocol. The subjects will be of either gender, between 18 and 65 years of age and suffering from confirmed discogenic LBP (minimum duration of 6 months) and are not suitable candidates for lumbar spinal surgery.

Subjects must meet all of the inclusion and none of the exclusion criteria to be enrolled in the post market pilot study. Subjects will read and sign an informed consent prior to data collection. Subjects will be recruited from the sites existing patient population and through new patient contacts as normally progresses in standard clinical practice.

4.2 Inclusion criteria

1. Subject of either gender between 18 and 65 years of age
2. Subject is able and willing to comply with the follow-up schedule and protocol
3. Subject is able to provide written informed consent
4. Chronic low back pain of at least 6 months
5. History consistent with discogenic low back pain (e.g. Pain produced on lumbar motion, significant functional limitation in sitting duration and tolerance)
6. Neurologic exam without marked motor deficit.
7. Definite/Highly Probable/Discogenic Pain as confirmed by provocative discography according to IASP/ISIS guidelines*
8. Low Back Pain intensity should be 6 or higher measured on a NPRS at baseline
9. Meets all the inclusion criteria for the implantation of a neurostimulation system as typically utilised in the study centre
10. Subject has been screened by a multi-disciplinary panel including a psychologist and deemed suitable for implantation

* Guidelines summarised in Appendix B

4.3 Exclusion criteria

1. Female subject of childbearing potential is pregnant/nursing or plans to become pregnant during the course of the study
2. Escalating or changing pain condition within the past month as evidenced by investigator examination
3. BMI ≥ 35
4. Subject has had injection therapy or radiofrequency treatment for their low back pain within the past 3 months
5. Subject currently has an active implantable device including ICD, pacemaker, spinal cord stimulator or intrathecal drug pump
6. Subject is unable to operate the device
7. Severe disc degeneration at the affected level as evidenced by $>50\%$ disc height loss on plain anteroposterior and lateral lumbar radiographs or CT/MRI.
8. Extruded or sequestered herniated nucleus pulposus at the affected level(s).
9. Previous lumbar back surgery (e.g. Laminectomy, discectomy or fusion) at the affected level(s)
10. Moderate to severe spinal stenosis due to osteophyte and/or ligamentous overgrowth as evidenced by MRI or CT in the previous 6 months
11. Moderate to severe endplate degenerative changes at the affected levels
12. Grade 1-2 spondylolisthesis
13. Previous Neurostimulation therapy

4.4 Sample size calculation

For this post market pilot study no formal sample size estimation has been made, we will enrol a maximum of 20 subjects.

5 TREATMENT OF SUBJECTS

5.1 Implant Procedure

The *Physician Implant Manual*, to be found in the packages of the components, provides a detailed description of the implant and surgical technique; this is also described briefly in Section 3. Following informed consent and baseline measurements, subjects will begin the two-phase treatment process in line with standard practice. Following INS insertion subjects will be followed prospectively for 12 months as shown in Figure 3.

As a result of the device design, the therapy is fully reversible and can be removed through a similar minor procedure.

5.2 Use of pre-existing therapies

Subjects will be allowed to continue using medication and other non-invasive therapies for the treatment of their pain condition. The Principal Investigators and/or sub-investigator as per standard of care will dictate the prescription of such treatments for pain.

6 DESCRIPTION OF THE DEVICE

6.1 Name and description of Neurostimulator System

The Spinal Modulation Neurostimulator System consists of the following components:

- Trial Neurostimulator
- Implantable Neurostimulator
- Trial Lead Kit
- Implant Lead Kit
- Connector Cable Kit
- Tunnelling Tool Kit
- Clinical Programmer
- Patient Programmer
- Auxiliary Magnet Kit
- Programmer Charger Kit
- Programmer Carrying case
- Lead Accessories Kit
- 22 cm Small Curve Delivery Sheath Kit
- 22 cm Big Curve Delivery Sheath Kit
- Lead Extension Kit

A detailed description of the components can be found in the Physician Implant Manual, included in the packages of the components.

On 16 November 2011, BSI granted Spinal Modulation, Inc. CE mark for the Spinal Modulation Neurostimulator System for the management of chronic intractable pain (CE 567069). The system has been registered with the CIBG in the Netherlands on 24 November 2011 and will be utilised within its CE marked indication.

6.2 Summary of known and potential risks and benefits of the therapy

A summary of the known and potential risks and benefits can be found in the accompanying manuals that are included in the package of the components. The general risks associated with the Spinal Modulation Neurostimulator System are similar to those associated with other Spinal Cord Stimulator systems. Possible risks to the subjects include both device and procedural based risks.

The most common side effects and risks are:

- Pain (where the needle is to be inserted)
- Pain caused by under stimulation due to lead migration
- Pain over the implantable neurostimulator site (only applicable in Phase 2)
- Escalating pain
- Bleeding (where the needle has been inserted)
- Headache
- Infection
- Localized collection of serous (clear) fluid at injection site
- Discomfort during the treatment
- Allergic or rejection response to implant materials
- Constant pain at the lead site
- Stimulation of the chest wall
- Lead migration (movement) and/or local skin breakage
- Weakness
- Clumsiness
- Numbness
- Temporary muscle activation

Very rare risks and side effects include:

- Cerebral Spinal Fluid (CSF) leakage
- Tissue damage
- Nerve damage
- Spinal cord compression
- Swelling
- Paralysis
- Hematoma
- Seroma
- Sensory loss
- Skin erosion around the INS or leads
- Battery failure and/or battery leakage
- Lead breakage requiring replacement of the lead
- Hardware malfunction requiring replacement of the neurostimulator
- Pain from a non-injurious stimulus to the skin (allodynia)
- An exaggerated sense of pain (hyperesthesia)

6.3 Device utilization

A detailed description of device utilization can be found in the Physician Implant Manual. Investigators involved in the study have been trained on the use of the Spinal Modulation Neurostimulator System and already have experience with the use of the commercially available products.

6.4 Devices

The devices that will be used in the post market observational pilot study are commercially available products, used within their licensed indication (intractable chronic pain). However, for this pilot study all devices and associated implantable equipment will be provided at no cost to the study centres as the device is not yet reimbursed for this specific subpopulation with CLBP.

The selected subjects will not be suitable candidates for lumbar spinal surgery and at the moment one of the requirements for reimbursement is having had a lumbar spinal surgery without success before receiving neurostimulation. A label of the products used will be added to the subject files to document and identify the devices.

Following completion of the study, any patient implanted during the course of the study will be eligible to receive free of charge replacement equipment, if necessary, while the therapy is still not reimbursed for CLBP. As soon as this indication will be reimbursed, equipment needs to be purchased in the usual manner.

7 METHODS

7.1 Assessments

During the scheduled follow-ups the following assessments will be performed. Table 1 in appendix A gives a detailed description of the assessments per follow-up.

- Pain, assessed by an 11 point (0-10) numerical pain rating scale (NPRS)
- Subject Satisfaction with treatment will be assessed using the Patient Global Impression of Change (PGIC), a 7 point Likert scale
 - R [REDACTED]
 - R [REDACTED]
 - R [REDACTED]
 - C [REDACTED]
 - C [REDACTED]
 - C [REDACTED]
 - S [REDACTED]
 - S [REDACTED]
 - R [REDACTED]
 - R [REDACTED]

7.2 Randomisation, blinding and treatment allocation

As this is a single-arm observational study, no randomisation or blinding will occur. All eligible subjects recruited into the study will undergo treatment in the usual manner and complete questionnaires at routinely scheduled follow up appointments. Subject who decided not to take part in this study will not receive a neurostimulator and will be monitored by their physician as needed in accordance with standard medical procedures.

7.3 Data Collection

During the post market pilot study, data will be collected on Case Report Forms (CRFs).

Subject Screening and baseline

Subjects presenting with discogenic CLBP of at least 6 months duration and not being suitable candidates for lumbar spinal surgery will be screened for possible entry into the post market pilot study. Subjects will be screened according to the Inclusion/Exclusion criteria and only subjects meeting all Inclusion criteria and none of the Exclusion criteria will be enrolled. The study will be explained to all subjects and subjects will provide informed consent prior to any data collection. Subjects will be allowed to discuss their participation in the study with the study physician, clinical staff, family, friends and personal or external physician.

Following subject screening and acquisition of Informed Consent, subjects will undergo a baseline assessment to collect clinical data prior to lead implantation and stimulation.

Trial Stimulation Lead Implant Procedure

Following collection of baseline measurements, subjects will begin Phase 1 of the two-step treatment process.

End of TNS Trial Phase

At the end of the Trial Phase, pain relief will be assessed to determine whether a subject should receive an INS implant. In line with standard clinical practice only subjects who experience $\geq 50\%$ pain relief during the trial phase will go on to receive the INS. The duration of the trial phase will be at the investigators discretion and in line with current, clinical practice (usually 5-10 days) but should be no longer than 30 days.

INS Implant Procedure

Eligible subjects willing to continue with the implant will undergo surgery to insert the fully implantable neurostimulator (INS). If the epidural leads were removed during the trial period, new leads will also be implanted at this time (see Physician Implant Manual for detailed information regarding the procedure). Each subject will receive a hand-held Patient Programmer that can be used to adjust stimulation amplitude as needed.

Regular Follow-ups

Subjects will be followed according to the follow-up schedule for 12 months following implant at regular intervals: 2-week (± 5 days), 3 month (± 2 weeks), 6 month (± 4 weeks) and 12 month (± 4 weeks). The given time-windows are advisable and coincide with routine follow up

visits for patients receiving treatment with DRG stimulation, therefore, visits outside the time windows will not be seen as a protocol deviation.

Prior to completing the required assessments, the subject will have his/her stimulator reprogrammed if needed (if applicable).

12-month follow-up (Study Exit)

The study will end 12 months following INS implantation. At this visit, the regular follow-up assessments as outlined in appendix A will be acquired and a trial exit form will be completed.

Following completion of the study, subjects will continue to use the Spinal Modulation Neurostimulator System. The subjects will be monitored by their physician as needed in accordance with standard medical procedures.

Interim Programming/Revision/Replacement/Explant (if necessary)

During the course of the study, subjects will have the option to return to the study site at any time to have their neurostimulator re-programmed to achieve maximal benefit. If any part of the Spinal Modulation Neurostimulator System becomes dysfunctional or requires adjustment following implantation, it is up to the investigator to perform an interim visit. In appendix A, the assessments for an interim visit and a revision are listed (if applicable).

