7.6 Follow-up of subjects withdrawn from the study

Subjects who are withdrawn will continue to receive normal, standard of care follow-up by the study physician.

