8.4 Follow-up of adverse events

All reported device related events will be followed until they have abated, or until a stable situation has been reached, unless the subject is lost to follow-up.

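### Subjects who have trial leads placed but receive no INS have no scheduled safety contact after End of Trial and no stated adverse-event collection window

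*Combined protocol and SAP*

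**What the plan says.** Treatment has two stages. In the first, for back pain, "epidural leads are implanted at the L2 and/or L1 level" and connected to an external stimulator (Section 3). Section 7.3 gives this trial phase a usual length of 5 to 10 days and an upper limit of 30. Only subjects with at least 50% relief proceed to an INS.

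The follow-up clock starts at that second stage. Section 3: "Following INS insertion subjects will be followed prospectively for 12 months as shown in Figure 3". Section 7.3, Regular Follow-ups: "Subjects will be followed according to the follow-up schedule for 12 months following implant at regular intervals", with visits at 2 weeks and at 3, 6 and 12 months. Section 7.3, Study Exit: "The study will end 12 months following INS implantation".

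On subjects who leave, Section 7.6 says: "Subjects who are withdrawn will continue to receive normal, standard of care follow-up by the study physician". On events, Section 8.4 says: "All reported device related events will be followed until they have abated, or until a stable situation has been reached". Section 8.1 limits investigator reporting to device-related AEs and SAEs and adds vigilance standards and the manufacturer's complaint procedures. Section 8.3 asks for reportable events to be documented for as long as the trial runs, without a per-subject end date.

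**The concern.** Safety is one of the purposes of data collection named in the Summary. The lead procedure is an exposure of its own, and every subject who enters the trial phase has it. Subjects who fail that phase carry the procedural risk without going on to the therapy. The Summary and Section 10.4 add that they would not be offered the therapy outside the study.

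Section 6.2 lists risks tied to the procedure rather than to long-term stimulation. Infection and "Localized collection of serous (clear) fluid at injection site" are among the common ones; CSF leakage, haematoma, seroma and nerve damage are among the very rare ones. The documents do not say when these become apparent. I assume that some can show after the leads are out, which the clinical team should confirm. If so, the schedule looks for late complications only in subjects who passed the trial phase. A late event that goes uncaptured in the others can only lower the complication count, and the results are meant to inform practice and future studies.

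**Working it through.** The plan states no event rate, safety sample size or safety denominator, and Section 4.4 says that no formal sample size estimate was made. There is no plan figure to reproduce. The check is a reading of the schedule, followed by arithmetic for scale.

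**1. Last scheduled contact without an INS.** Visits and study end are all timed from INS implant (Sections 3 and 7.3). With no implant date, none of them can be scheduled. The last contact the text provides is End of Trial.

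**2. Other routes into the data after that point.**
- Section 8.3 covers the duration of the trial, but no trial end is defined for a subject without an INS.
- Section 8.4 follows events already reported; it does not look for new ones.
- Section 7.6 provides standard care by the study physician and is silent on case report forms. Section 7.4 describes withdrawal as the subject leaving or the investigator deciding on urgent medical grounds, so it is not even clear that a trial failure counts as withdrawn.
- Section 7.7 sits under premature termination and ties monitoring to the life of the device. A subject whose leads are out has none.
- Section 8.1 leaves vigilance and complaint reporting open. That depends on someone raising the event, and it sets no collection window.
- Interim visits in Section 7.3 serve reprogramming, or a system that needs attention after implantation.
- Appendix A makes the AE and SAE forms available as needed in every column, including Trial Procedure and End of Trial. Events up to End of Trial can therefore be captured.

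None of these sets a window for an event that starts after lead removal in a subject without an INS.

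**3. Number affected.** Inputs from Section 4.1: at most 20 enrolled; enrolment stops at 15 implanted; those already enrolled continue.
- 20 trialled and 15 implanted: 20 − 15 = 5, and 5/20 = 25%.
- First 15 trialled all succeed and no one else is enrolled: 0 of 15.
- Trial success rate s, assumed because the documents give none, with all 20 trialled: expected number without INS = 20 × (1 − s). This gives 10 for s = 50%, 8 for 60%, 5 for 75% and 2 for 90%. The stop at 15 implants makes the number smaller when s is high.

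The figure of about 50% in Section 1.2 is not a trial success rate. It describes treatment success among patients who had already passed a trial.

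**4. Scheduled observation.** At most 30 days from lead placement, against 12 months after implant: 30/365 = 8.2%. At the usual 5 to 10 days: 5/365 = 1.4% to 10/365 = 2.7%.

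**5. What complete follow-up would add.** If n subjects are followed and none has a late complication, the one-sided 95% upper bound on the rate is 1 − 0.05^(1/n).
- n = 15: 1 − 0.05^(1/15) = 18.1%
- n = 20: 1 − 0.05^(1/20) = 13.9%

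**6. Chance that there is something to miss.** For an assumed late complication rate p (not in the documents), the chance of at least one event among 5 subjects is 1 − (1 − p)^5.
- p = 2%: 9.6%
- p = 5%: 22.6%
- p = 10%: 41.0%

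**The case against.** In favour of the plan as written, trial-phase events are captured as they occur, subjects stay under a study physician who must report device-related events, and vigilance and complaint procedures apply whatever the visit schedule. The primary objective concerns implanted subjects only, and this is a small descriptive pilot. Figure 3, the study flowchart, was not available to me, and several Appendix A cells are unreadable; either could show what happens to trial failures.

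Most of this stands as a limit on the point. Three stronger readings that a reader might infer are not supported:

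- **That later complications are never recorded.** Sections 7.6, 8.1, 8.3 and 8.4 leave routes open. The text supports only that recording in the study data is not assured.
- **That explanted subjects leave safety collection.** Section 7.3 treats explant as an interim event, and nothing there ends the 12-month follow-up because of it. Their status is simply not stated.
- **That Appendix A shows trial failures exiting at End of Trial.** As it reads in the available text, the Trial Exit row has its required mark under the 6-month visit, while Section 7.3 places exit at 12 months. The row appears shifted, so its marks under End of Trial and Revision cannot carry the argument.

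A downward bias of any given size is not shown either, since no late-event rate and no safety denominator are stated. What survives needs neither the table nor the figure: the text of Sections 3 and 7.3 provides no scheduled contact after End of Trial for a subject without an INS, and Section 8 sets no collection window.

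**Conclusion.** The point holds for subjects who have leads placed but do not receive an INS. Followed as written, the schedule gives them at most about 30 days of planned observation, against 12 months after implant for the others, in a study that sets out to collect safety data. For explanted subjects the defect is narrower: the plan does not say whether they stay in scheduled follow-up.

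The size is uncertain. The figure of 5 of 20 (25%) assumes full enrolment, every enrolled subject trialled and exactly 15 implanted; the range runs from 0 of 15 to more than 5. That any late complication would be missed rests on assumed rates and on a clinical judgement about timing that the documents do not give. The primary objective is untouched. The gap merits a small amendment because it concerns the only subjects with procedural exposure and no scheduled later contact, and because it is cheap to close.

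**What to change.** In Section 7.3 and Appendix A:

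- State when subjects without an INS exit the study, and that explanted subjects remain in scheduled safety follow-up.
- Add one safety data-collection contact for every subject without an INS, at a fixed interval after final lead removal (e.g. 30 days). It can be a telephone call or an existing routine visit, with the AE/SAE forms completed.
- Complete the Trial Exit form after that contact.

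In Section 9, report device-related complications over all subjects who had a lead procedure, alongside the implanted subset.

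This changes data collection only. It needs a short amendment and one call or visit record for each non-implanted subject: 5 in the 20-and-15 case, and up to 10 if trial success is assumed to be as low as 50%. No new procedure or staff is required. The downside is that exit is delayed by a few weeks for a few subjects and the reported complication count may be slightly higher.
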